## **9.0 DATA AND SPECIMENS (REQUIRED)**

### **a) Handling of Data and Specimens**

All contact information collected from the study, including name, mailing address, phone number and email address, will be stored on an encrypted and password protected computer drive in the OHSU Knight Cancer Research Building that only IRB approved persons have access to.

All other data collected for this study including answers from the health history form (e.g. DOB, education, income, demographics, as well as cancer specific information such as diagnosis, type & dates of cancer treatments), answers to the study surveys, and results from the physical tests will be stored in OCTRI's installation of REDCap, a highly secure and robust web-based research data collection and management system.

Data that may be collected from a patient's electronic medical record would include contact information including phone number, mailing address and email address, as well as cancer specific information such as diagnosis, type & dates of cancer treatments. Any data collected will be stored on an encrypted and password protected computer drive in the OHSU Knight Cancer Research Building that only IRB approved persons have access to.

Consent forms and any surveys that were filled out on paper will be stored in a locked cabinet in a locked, secure room in the Knight Cancer Research Building. Documentation of the consent process and a copy of the signed consent will be maintained in the patient's medical record.

Data from the HHQ, surveys and physical tests will be transported by secure electronic transmission (i.e. secure, encrypted email or stored on a secure shared drive such as Box).

The PI will be responsible for the receipt or transmission of the data.

Data used and collected for purposes of this study will be stored until data analysis is complete and then the data will be transferred to a repository. All data received from OSCaR for purposes of eligibility/recruitment purposes will be destroyed after the purposes of the research have been fulfilled. Electronic files will be deleted from the secured drive used by the study team.

### **b) Sharing of Results with Subjects**

Results of the physical tests will be shared with the subjects

### **c) Data and Specimen Banking**

Specimens and data from this study will be banked in a repository for future use as part of this protocol. Data may be stored indefinitely while blood samples will be stored for no more than 20 years. Access to data/specimens is restricted to study personnel.

Data/specimens released to other investigators will be labeled with only the code assigned to each participant at enrollment. This same unique identifier, along with the date of specimen collection, will be used to label blood samples taken and for storage.

After the study is complete, all contact information (e.g., name, mailing address, phone number) and data from the HHQ, study surveys and physical tests will be stored in a private locked-repository (IRB# 7553) at OHSU Knight Cancer Research Building. The contact information will be stored separately from the other data. The repository will be managed by [name], the Principal Investigator of the study. All of the data from the surveys and physical tests will be coded with a unique ID number that doesn't contain any

PHI. The list matching the PHI and the ID number is stored in a password protected document on a password protected computer drive in the OHSU Knight Cancer Research Building that only IRB approved persons have access to. Only IRB approved research staff will have access to the password and computer drive where this record is stored. Any requests made for the use of the data will be evaluated by the repository guardian, [name], who will create a subset of eligible data using OHSU IRB confidentiality procedures. The repository guardian will apply an algorithm to the ID numbers on the data subset, therefore, creating a new unique identifier for each data that will be used. This will ensure that only the guardian can link the data back to original study ID numbers and corresponding PHI. Only the guardian will have access to this algorithm. Any future human subject research study that wants to use the data or contact information from the repository will require separate IRB approval. The usage requirements will be limited to the principal investigator, co-investigators and associates from the original research studies. Any future study requesting use of the data must either be related to the original research study or explore new and innovative research questions approved by the guardian.

## **10.0 RISKS TO SUBJECTS**

The risks to human subjects include potential adverse effects of exercise. Risks of participation include tiredness from answering research questions or participating in exercise, anxiety about ability to read surveys or reach exercise goals, discouragement about ability to exercise, worry about loss of confidentiality/privacy, and perception of coercion to participate. Additional risks to participation include phlebotomy and radiation exposure. With respect to venipuncture procedures in general, some participants may experience temporary discomfort. Extremely rare risks associated with venipuncture are bleeding, fainting or feeling lightheaded, hematoma, or infection. With respect to radiation exposure, there is minimal radiation exposure associated with a whole body DXA scan (<1  $\mu$ Sv), which is less than half of radiation received on a one-way trip from California to New York and has negligible health risks.

Ancillary study: Participants in the ancillary study will not incur risks from phlebotomy or radiation exposure. Participants in the ancillary study may be provided with an internet-capable device (i.e. Chromebook or tablet) to help them access the study, and use of the device may pose a risk of loss of confidentiality/privacy.

### **Adequacy of Protection Against Risks**

#### **a. Recruitment and Informed Consent**

The Oregon State Cancer Registry (OSCaR) will be the primary means used to recruit participants. Established in 1996, the registry is nationally recognized for the accuracy and completeness of its data. All tumors, except common skin cancers, are required to be reported by hospital registries, clinics, cancer treatment centers, and physician offices in Oregon and neighboring states where Oregon residents are treated. Patient's data is reported, checked for quality assurance, and entered into OSCaR within six months of diagnosis. OSCaR procedures are well established and designed to protect persons in the registry. When each person's data is entered in the registry, the individual is sent a letter asking if he is willing to be contacted about opportunities to participate in research studies. Very few refuse to be contacted.

Potential participants will be identified by OSCaR for their cancer type (prostate, breast, colorectal), cancer treatment (surgery, radiation and/or chemotherapy), age, and zip code. OSCaR will then send identified patient data including the patient's physician information to our team using secure electronic transmission (i.e. encrypted flashdrive, secure encrypted email or stored on a secure shared drive such as Box). Data from OSCaR is only being used for purposes

of identifying eligible patients and from this point forward is no longer involved in the research. Our team will then send an information letter about the study to listed physicians for identified persons in the registry, notifying the physician that their patient will be sent information about the study. Physicians who determine that their patients should not receive study information are asked to return a form to the study investigator within a 3-week period. These persons will no longer be considered eligible to receive study information. All other potential participants will be sent an information letter briefly describing the study along with a response form and contact information of the research team. Persons who are interested in receiving more information about the study are asked to either contact our team directly (phone, email, text) or complete the response form and return it to our team. For all response forms returned to our team and in response to all other forms of inquiry, a member of the research staff will then contact interested persons to provide more study information to them and to screen for eligibility if they indicate a willingness to participate.

Potential participants will also be recruited via a study information mailing through the OHSU Cancer Registry and interested participants will contact us if they would like to learn more about the study and to check for eligibility. In addition we will recruit at community events, such as patient conferences and fundraisers, through study advertisements placed through various media outlets (i.e., internet, newspaper, radio), and by referral from the OHSU Prostate Cancer Clinic.

Ancillary study: Participants may also be recruited through the Oregon Office of Rural Health or the Oregon Rural Practice-based Research Network.

Members of the research team, will consult on eligibility issues as needed during recruitment. Eligible persons will come to the OHSU Knight Cancer Research Building to be consented and undergo baseline measures. Participants will also visit the OHSU Oregon Clinical Translational Institute for a blood draw collection at each measurement point.

Ancillary study: Participants in the ancillary study will participate remotely and will not visit OHSU.

### **b. Protection Against Risk**

As with any form of exercise, there is a slight risk of injury. We have not had a single participant drop out of a study due to an injury related to the exercise program; however, as with any study in older adults, exercise adherence has been affected by minor musculoskeletal complaints and are typically exacerbations of pre-existing orthopedic conditions. We will take the following steps to reduce the risk of injury and symptoms/side from exercise training: 1) Physician clearance: We will send a notice to each participant's oncologist (or primary care provider) asking him or her to clear the participant for participation in any of the study exercise programs prior to beginning exercise training. If a wo/man's physician does not clear him for participation we will inform the participant and refer him/her to her physician for clarification of the decision, 2) Monitor for and treat early musculoskeletal symptoms: From experience in our prior trials we have developed an injury prevention education and monitoring program. At the beginning of each participant's start in the intervention he is provided general injury prevention information from the Project Director and exercise trainer. During the intervention the exercise trainer will consult with the Project Director on any reported exercise-related injuries and/or physical complaints from participants that affects their ability to do their exercise program. The Project Director will consult with participants on an individual basis, as needed, and will advise on treatment of their injury/complaint and when referral to a health practitioner is appropriate. *The Project Director will work with the study team to document and track minor and major complaints and injuries in order*

*to evaluate the overall safety and appropriateness of the study interventions for the study population.*

During testing visits, if a participant experiences tiredness, s/he will be told s/he can stop answering research questions, or participating in performance or clinical testing, and begin again at a later time. If tiredness occurs during exercise sessions, participants may rest as often as needed. If a participant is anxious about ability to read surveys, we will offer to ask the questions verbally and fill out the survey by telephone, if anxious about ability to reach exercise goals or discouraged about ability to exercise, Project Director, in consultation with the PI [name], will problem-solve and support the participant in changing goals or developing alternative methods to meet goals. If a participant is worried about privacy and confidentiality of data, the Project Manager will discuss the methods for maintaining confidentiality: individual data will be identified only by a study ID number and only one computer file will link ID numbers with identifiable data; all computer records will be protected by a password known only to authorized study personnel; paper documents, such as surveys or computer disks, will be kept in locked files, and results will presented as group data only. To prevent the perception of coercion to participate, participants will be told they may decide to discontinue participation in the study at any time, that non-participation will not affect their usual care at their local clinic or at OHSU, and that data on non-participation will be kept confidential, using the methods described above.

During remote exercise and testing sessions, additional safety precautions will include: 1) Providing safety recommendations specific to exercises and/or assessments (i.e., standing near a wall for balance activities) 2) Adapting the exercise protocol as necessary (ie. limit weight.) 3) Verifying address of remote exercise location (i.e., home address), should the exercise instructor or Research Assistant need to call 911 in an emergency 4) Ensuring that emergency contact information is up-to-date and readily available.

To minimize risks associated with phlebotomy, all venipuncture will be conducted by trained personnel from the Oregon Clinical Translational Research Institute (OCTRI) nursing services staff in adherence with OHSU Patient Care Services policy on venipuncture techniques for blood sampling. Serum samples will be labeled with participants unique study identifiers and will be subsequently stored in the OCTRI core laboratory. OCTRI is supported by the NIH specifically for the purposes of translational research, and the OCTRI core laboratory performs all procedures in accordance with guidelines issued by the Clinical and Laboratory Standards Institute, American Association for Clinical Chemistry, American Society for Clinical Pathology and other professional organizations appropriate to each specialty. To minimize risk against excess radiation exposure from DXA, whole body DXA scans will be conducted by the RA who will have been trained by the Principal Investigator and/or Project Director. Whole body DXA scans will be performed according to standard protocols which allows for early repositioning to minimize patient exposure.

Ancillary study: Participants in the ancillary study will not incur risks from phlebotomy or radiation exposure.

Participants in the ancillary study may be provided with an internet-capable device (i.e. Chromebook or tablet) to videoconference with the research team. To minimize risks to participant confidentiality/privacy, participants will be asked to only use the device for study-related activities, and we will recommend that participants lock the device with a password when not in use.

## **11.0 POTENTIAL BENEFITS TO SUBJECTS**

Participants may or may not personally benefit from being in this study.

## 12.0 TIMELINE & MILESTONES

Project Timetable	Y1				Y2				Y3				Y4				Y5			
	Q1	Q2	Q3	Q4	Q1	Q2	Q3	Q4												
Finalize protocols, databases	X	X																		
Hire/train research assistants	X	X																		
Hire/train exercise instructors		X				X					X						X			
Recruit, enroll, baseline visit			W1	W2	W3	W4			W5	W6	W7	WG	W8	W9			W10			
Start 6-month intervention			W1	W2	W3	W4			W5	W6	W7	WG	W8	W9			W10			
Mid- & post-intervention visits				X	X	X	X		X	X	X	X	X	X		X	X	X	X	
6-month follow up visit					X	X	X	X	X	X	X	X	X	X		X	X	X	X	X
Data cleaning and analysis						X	X	X	X	X	X	X	X	X		X	X	X	X	X
Present and publish results																			X	X

Participants are recruited in 10 waves (W1, W2, ...); WG = geographically underserved wave (ancillary study); Quarters are approximate time points

## 13.0 BIO-STATISTICAL CONSIDERATIONS

### Power and Sample Size

Required sample size was derived for the outcomes of Aim 1. Power analysis using traditional assumptions of the repeated measures ANOVA model suggest that as few as 174 couples would be necessary to detect a small effect ( $d=.20$ ) between groups over time, an effect smaller than the observed effect on affectionate behavior in spouses/partners in our previous work[40]. However, these traditional power calculations are known to be optimistic. While there are good power formulae for MLM clustered designs and repeated measures designs, as yet there is no specific formula for calculating power for dyadic analyses. Using a formula provided by Raudenbush and Bryk[104, 105] for individual repeated measures and estimates from our previous dyadic models, we calculate a sample of 264 couples measured 4 times over a 12-month period has a power of 0.80 to detect a moderate effect ( $d=.40$ ) on change over time. As dyad models using MLM control for interdependence between members of the couple, power is increased over an individual model. We, therefore, believe this to be a more conservative estimate of power. Further attempts to increase power and reduce Type I error will be to use the omnibus hypothesis-testing procedure in the HLM program. Another rule-of-thumb is to require a minimum number of subjects per parameter estimated. Even in the most complicated model, the proposed sample of 264 couples would exceed the minimum standard of 5-10 subjects per parameter estimated.[106] No universal approach has been adopted for sample size considerations in GMM and this will be used in an exploratory aim; however, our n-to-items ratio exceeds sample size recommendations for related approaches (10-20:1).[107] In sum, the proposed sample size of 264 couples is on par with our previous trials and will allow us to detect clinically meaningful change and address study aims. To insulate the sample size against an estimated attrition of 10% across the study period, 294 couples will be randomized. The attrition estimate is more conservative than our prior trial of *Exercising Together* where no couples in the exercise program dropped out and the drop out in our current GET FIT trial that average 6% for a 6-month intervention. Couples will be enrolled into 10 waves (a new wave begins every 3-4 months) of 9-10 couples to maintain reasonable class sizes and make efficient use of testing resources. We will recruit approximately even numbers of couples coping with each type of cancer (N=98 per disease site) and stratify by cancer type at randomization.

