will lead to better physical, mental and relational health within the dyad. As a next step toward broader dissemination, we need to know if a couples-based exercise approach is similarly effective for couples coping with other cancers (and when survivor gender varies), early in the illness trajectory when a couple's relationship is most vulnerable, and at reducing risk factors for chronic illness in both partners. An equally important next step is to distinguish the unique benefits of partnered training on individual and couple health from the possible benefits of exercising in a group with others and/or of engaging both partners in a new health behavior. We propose a larger, more rigorous trial of *Exercising Together*, expanding to include couples coping early on with PC, BC or CRC, clinical markers of chronic disease risk, and comparison groups that can test the unique benefits of partnered training.

Additional background for ancillary study: Rural cancer survivors are at greater risk for a variety of poor health outcomes, even many years after their cancer diagnosis, but are the least likely to have access to programs and resources to improve their health and well-being. Improving health behaviors, such as physical activity, can have a substantial impact on quality of life and survival in cancer survivors and their partners, but rural and poor adults, and particularly cancer survivors, have low rates of physical activity. Survivors living in rural areas and/or in poverty face many barriers to exercise, particularly facility-based, supervised programs which can provide a more effective, safe and supportive engaging environment than unsupervised training. There are no studies of supervised group exercise in rural and poor cancer survivors and no studies at all, even distance-based programs, that target partners and the couple as a whole. Given our successful adaptation of *Exercising Together* to remote delivery during the COVID 19 pandemic, we may be able to extend our programs to couples coping with cancer who would never be able to participate in our parent trial.

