Aim 1: Determine the efficacy of partnered strength training on relationship quality (intimacy, communication and incongruence). A longitudinal multivariate-outcomes dyad model will be used to directly examine couple trajectories in intimacy (emotional & physical) and communication over time. This is a multi-level model where responses from the survivor and spouse/partner are modeled simultaneously to control for the interdependent nature of the data and autocorrelation among repeated assessments. These models have been described and used extensively by Co-PI [name].[22, 111-113] The Level 1 model has four coefficients representing intercepts (baseline assessments) and slopes (rates of change) for survivors and spouses/partners that become outcome variables in a Level 2 model. Models with linear and quadratic change across time will be compared to determine best fit to the data. Aim 1 will be addressed with Level-2 models that include dummy variables to directly examine the effects of the partnered intervention vs. supervised individual (dummy 1) and unsupervised individual (dummy 2) exercise groups on individual level changes (controlling for couple effects) in intimacy and communication across time. A significant group coefficient on the slopes at level 2 and significantly better fitting model (evidenced by deviance statistic) will indicate the rate of change across time is different depending on a treatment group (i.e., interaction effect). We will also explore the efficacy of *Exercising Together* on incongruence (regarding survivor pain & fatigue) in couples. Univariate-outcomes models will be used to generate Empirical Bayes estimates of the gap between survivor and spouse/partner over time for each symptom measure. This comprehensive approach to estimating incongruence has been described elsewhere[114-116] and successfully used by this team.[55, 63, 113, 117, 118] The effect of *Exercising Together* on incongruence will be directly tested (similar to above model) by a significant coefficient for one of the two GROUP variables on the slope parameter and significantly better fitting model.

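### Does giving power 0.80 only for d = 0.40, without its inputs, beside a figure of 174 couples for d = 0.20, undermine the sample size?

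*Combined protocol and SAP*

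**What the plan says.** Section 13.0, Power and Sample Size, gives two calculations. Under conventional repeated-measures ANOVA assumptions, "as few as 174 couples would be necessary to detect a small effect" (d = 0.20), described as "an effect smaller than the observed effect on affectionate behavior in spouses/partners in our previous work". The next sentence sets this aside: "these traditional power calculations are known to be optimistic". The plan then applies a published formula for individual repeated measures, with estimates from the team's earlier dyadic models, and reports that "we calculate a sample of 264 couples measured 4 times over a 12-month period has a power of 0.80 to detect a moderate effect" (d = 0.40). It adds, because a dyadic model accounts for interdependence within couples: "We, therefore, believe this to be a more conservative estimate of power". Allowing for 10% attrition, 294 couples are randomised. The paragraph concludes that the sample "will allow us to detect clinically meaningful change and address study aims".

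The Aim 1 model in the Analysis Plan uses "dummy variables to directly examine the effects of the partnered intervention vs. supervised individual (dummy 1) and unsupervised individual (dummy 2) exercise groups". The power paragraph does not say whether 0.80 applies to each of these contrasts, to both jointly, or to something else.

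**The concern.** Three things look wrong at first.

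- **The 0.80 cannot be checked.** The significance level, the number of sides, the SD behind d, the variance components and the contrast are all absent. Nor does the paragraph justify d = 0.40 or define the change it regards as clinically meaningful.
- **The two calculations seem to conflict.** A small effect appears to need 174 couples while a moderate one needs 264. On a common scale, halving d should quadruple the number.
- **The true difference may be small.** All three arms follow the same basic strength programme (Section 3.0, Study Arms), and Section 1.0 wants to "distinguish the unique benefits of partnered training on individual and couple health from the possible benefits of exercising in a group with others". If the added effect of partnering were d = 0.20 and power there were about 0.3, the trial would miss it about 7 times in 10. A null result could then be misread as showing that partnering adds nothing.

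**Working it through.** **Inputs.** From Section 13.0: 264 couples analysed, 4 measurements over 12 months, power 0.80 at d = 0.40, 174 couples at d = 0.20, attrition 10%. From Section 8.0: three arms with even allocation, taken as 88 couples per arm analysed. Assumed because not stated: 5% significance level, two-sided unless noted.

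**Step 1. Attrition.** 264 / 0.9 = 293.3, rounded up to 294. This agrees with the plan.

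**Step 2. Is 0.80 at d = 0.40 plausible?** Take d in SDs of change, unadjusted and measured without error. Power = Φ(d·√(n₁n₂/(n₁+n₂)) − z), with z = 1.960 (two-sided) or 1.645 (one-sided).

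| Comparison | d·√(n₁n₂/(n₁+n₂)) | Two-sided | One-sided |
|---|---|---|---|
| 88 v 88 | 0.40 × √44 = 2.653 | 0.756 | 0.843 |
| 98 v 98 (as randomised) | 0.40 × √49 = 2.800 | 0.800 | 0.876 |
| 88 v 176 (comparators pooled) | 0.40 × √58.67 = 3.064 | 0.865 | 0.922 |
| 132 v 132 | 0.40 × √66 = 3.250 | 0.901 | 0.946 |

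The two-group slope formula with noncentrality J·d²·reliability/4 gives 264 × 0.16 × 0.75 / 4 = 7.92 for J = 264 and reliability 0.75, hence power 0.80. For a single pair of arms (J = 176) its maximum, at reliability 1, is 0.751. So 0.80 lies inside the range of reasonable readings. The missing inputs prevent confirmation, but nothing contradicts the figure.

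**Step 3. The 174.** Use the group-by-time F test with k = 3 arms, m = 4 visits, f = d/2 = 0.10 and correlation 0.5. Then λ = f²·N·m/(1 − 0.5), df₁ = (k−1)(m−1) = 6 and df₂ = (N−3)·3.

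- N = 174: λ = 0.01 × 174 × 4 / 0.5 = 13.92, df₂ = 513, power 0.804.
- N = 171: λ = 13.68, df₂ = 504, power 0.796.

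So 174 is the smallest number divisible by three that reaches 0.80. The inputs were inferred by matching the answer: correlation 0.4 gives 207 in equal arms, and 0.6 gives 141. The match is persuasive but not proof of what the sponsor did.

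**Step 4. What 0.80 at d = 0.40 implies at smaller d.** Within one calculation the noncentrality scales with d². For a single two-sided contrast, 1.960 + 0.842 = 2.802.

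- d = 0.30: 2.802 × 0.75 = 2.101, power Φ(2.101 − 1.960) = 0.556.
- d = 0.20: 2.802 × 0.5 = 1.401, power Φ(1.401 − 1.960) = 0.288.

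Other 5% tests give, at d = 0.20, 0.265 (2 df), 0.243 (4 df) and 0.344 (one-sided). This scaling is correct, but only if d means the same thing at both values.

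**Step 5. Do the two d values share a scale?** Probably not, if Step 3 describes what was done. Suppose Exercising Together departs linearly from two equal comparators. The variance of the arm pattern (1, 0, 0) is 2/9 = 0.2222, and that of the time pattern (0, 0.25, 0.5, 1) is 0.1367. Then f = 0.10 corresponds to 0.10 / √(0.2222 × 0.1367) = 0.574 SD in 12-month change.

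The conversion depends on the time course. If the effect peaks at 6 months and halves by 12 (0, 0.5, 1, 0.5; variance 0.125), the peak difference is 0.10 / √(0.2222 × 0.125) = 0.60 SD and the 12-month difference 0.30 SD. So 174 couples at d = 0.20 and 264 at d = 0.40 need not be inconsistent, and setting 4 × 264 = 1,056 against 174 compares unlike quantities.

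**The case for a change.** The best case for a change is that the contrast matters. If 0.80 was worked out for Exercising Together against both comparators pooled, the same inputs give each pairwise contrast 2.802 × √(44/58.67) = 2.427, power 0.68. If it was worked out for 264 couples in two equal groups, each pairwise contrast has 2.802 × √(88/132) = 2.288, power 0.63. The plan's caveat of optimism does not tell the reader that the 174 may rest on a different test and effect scale. The sentence on clinically meaningful change has no defined target behind it. Stating the inputs would cost the sponsor little.

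Much of this stands as comment on reporting. The inputs, the contrast, the scale of d and the reason for d = 0.40 are absent, and a fuller paragraph would be better.

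It does not establish an error. The lower pairwise figures depend on which contrast was used, and that is unknown. The pairwise reading is equally open, and the plan expects some gain from the dyadic model. The 174 is a correct output of a standard calculation. Nor is d = 0.20 the pilot estimate: the plan says only that it is smaller than a pilot effect whose size is not given, and that effect could be 0.40 or more. Printing 0.56 and 0.29 in the plan would rest on an assumed significance level, contrast and common scale that the sponsor has not confirmed.

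**Conclusion.** No change to the plan is needed. The paragraph omits detail, but neither of its figures is shown to be wrong. With 88 couples per arm, power at d = 0.40 is 0.76 two-sided or 0.84 one-sided on the simplest reading, so 0.80 is credible. The 174 reproduces, the plan itself discounts it, and no design decision rests on it.

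Power of about 0.29 at d = 0.20 (0.24 to 0.34 across the 5% tests considered) assumes that 0.80 is exact and that d is on one scale throughout. Even then it describes an effect for which the 264-couple calculation claims no power. A trial sized for a moderate difference between exercising arms accepts that trade-off.

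Supplying the missing inputs would alter no enrolment number, model, contrast or reported estimate. The risk of over-reading a null result is met at reporting, where the confidence interval for each contrast shows which differences remain possible. The plan nowhere says that it would treat non-significance as evidence of no added benefit.
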